5.3.5 Missing Data

Missing data will be imputed such that the patient with missing data will have no change from baseline on the missing outcome. This can be considered a worst-case imputation strategy for the CPAP treatment.

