3.3 Analysis Populations

The Enrolled set will include all patients who have provided informed consent and have been included into the study data base.

The Full Analysis Set (FAS) will be defined as all patients randomly assigned to a treatment group.

The Per Protocol Set (PPS) will include all randomised patients who have at least one assessment of the efficacy variable burden of atrial fibrillation, are on their randomized treatment CPAP or usual care. In the CPAP group, patients with no duration of the CPAP device the last three months will be excluded for the PPS.

4 Trial Population

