4.1 Screening Data, Eligibility and Recruitment

The total number of screened patients and reasons for not entering the trial will be summarised and tabulated.

A CONSORT flow diagram (appendix A) will be used to summarise the number of patients who were:

- assessed for eligibility at screening
- eligible at screening
- ineligible at screening*
- eligible and randomised
- eligible but not randomised*

STATISTICAL ANALYSIS PLAN for Effect of treatment of sleep apnea in patients with paroxysmal atrial fibrillation.

- received the randomised allocation
- did not receive the randomised allocation*
- lost to follow-up*
- discontinued the intervention*
- randomised and included in the primary analysis
- randomised and excluded from the primary analysis*

*reasons will be provided.

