5.3 Analysis Methods

5.3.1 Primary Outcome

The primary outcome, difference between CPAP and usual care in change in AF burden from baseline to the last three months of the intervention period will be analysed with linear regression, with AF burden last three months as the dependent variable and treatment (CPAP vs usual care), study site (St Olavs University Hospital, Trondheim vs Rikshospitalet,

STATISTICAL ANALYSIS PLAN for Effect of treatment of sleep apnea in patients with paroxysmal atrial fibrillation.

Oslo), and AF burden at baseline as explanatory variables. The mean difference between the two treatment groups with a 95% confidence interval will be reported, together with a P-value for the null hypothesis of no treatment difference.

The primary analysis will be done on the Full Analysis Set. A secondary analysis will be done on the Per Protocol Set.

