5.3.2 Secondary Continuous Outcomes

All secondary continuous outcomes (see table in Section 5.1.4) will be analysed in the same manner as the primary outcome, with linear regression with the last measurement as the dependent variable and treatment, study site, and baseline measurement as explanatory variables. The results will be reported as the mean treatment difference with a 95% confidence interval, and P-value for the null hypothesis of no treatment difference.

All secondary continuous outcomes will be analysed on the Full Analysis Set.

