5.3.4 Assumption Checks and Alternative Analyses

The assumption of normally distributed residuals in linear regression will be checked by plotting histograms of the residuals and examining their descriptive statistics, such as mean, median, standard deviation, and coefficient of skewness.

In cases where the distribution of the residuals is deemed to deviate too much from the normal distribution to allow linear regression to be used, a median regression (i.e. a quantile regression) will be performed instead of the linear regression. Then, the difference in medians (with a 95% confidence interval and a P-value for equality of medians) will be reported instead of the difference in means.

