5.3.6 Sensitivity Analyses

1. The primary outcome will be analysed on the Per Protocol Set.
2. Missing data will be imputed with the mean change in the respective treatment group. I.e., a patient in the CPAP group with missing data will be given a change for

STATISTICAL ANALYSIS PLAN for Effect of treatment of sleep apnea in patients with paroxysmal atrial fibrillation.

the missing outcome equal to the mean change in the CPAP group, and vice versa for patients in the usual care group.

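### The no-change imputation rule is labelled worst-case for CPAP, but it is not guaranteed to be conservative, and no planned analysis tests a case worse for CPAP

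*SAP*

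**What the plan says.** SAP 5.3.5 sets one rule: "Missing data will be imputed such that the patient with missing data will have no change from baseline on the missing outcome". It names no arm, so it applies to both. The next sentence gives the justification: "This can be considered a worst-case imputation strategy for the CPAP treatment".

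The rule reaches the main result. SAP 5.3.1 states "The primary analysis will be done on the Full Analysis Set", and SAP 3.3 states "The Full Analysis Set (FAS) will be defined as all patients randomly assigned to a treatment group". It also reaches the secondary outcomes; for the continuous ones SAP 5.3.2 says "All secondary continuous outcomes will be analysed on the Full Analysis Set".

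SAP 5.3.6 plans two checks. One is the Per Protocol Set. The other is a second single imputation: "Missing data will be imputed with the mean change in the respective treatment group". SAP 5.3.4 adds that if residuals are too far from normal, "a median regression (i.e. a quantile regression) will be performed instead of the linear regression".

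**The concern.** A worst case for CPAP has to let missing CPAP patients do worse than missing controls. This rule treats them alike and never lets a missing CPAP patient worsen. Whether it works for or against CPAP depends on how burden changes in both arms, on which arm has more missing data, and on who is missing.

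The documents foresee change unrelated to CPAP. All participants receive lifestyle advice (protocol 4.3), and cardioversion or new antiarrhythmic drugs after inclusion are anticipated (SAP 5.3.7). Neither passage gives a size or a direction of net change.

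At stake is the claim attached to a positive result: it could be reported as conservative when the rule does not guarantee that.

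**Working it through.** **Inputs from SAP 2.1 and 2.3.** 50 patients per arm; mean burden 34% of time; target a 25% relative reduction, 0.25 × 34 = 8.5 percentage points; SD 12, allowed to rise to 15; two-sided 5%, power 80%. These reproduce the SAP's sample size: SD 12 needs 32 per arm by the normal approximation and 33 by the t-test; SD 15 needs 49 and 50, hence 100 in total.

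**Assumed, because the documents give no value.** Missing fractions of 5% to 20% per arm, a common change of 0, 4 or 8.5 points, and a baseline-to-follow-up correlation of 0.5.

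**Algebra.** Let d be the common fall, e the extra fall with CPAP, and mC and mT the fractions missing in control and CPAP. If missingness is unrelated to baseline within arm, the no-change rule estimates (1 − mT)(d + e) − (1 − mC)d. Subtracting the true effect e gives

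bias towards CPAP = d(mC − mT) − e·mT.

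- Planning case, d = 0, e = 8.5, 10% missing per arm: −0.85, so the estimate is 7.65. Conservative, as the SAP intends.
- No effect, d = 4, mC = 0.10, mT = 0.05: 4 × 0.05 = +0.20.
- No effect, d = 8.5, mC = 0.20, mT = 0.05: 8.5 × 0.15 = +1.28.
- No effect, burden rising 8.5 (d = −8.5), mC = 0.05, mT = 0.20: +1.28.
- e = 8.5, d = 8.5, mC = 0.20, mT = 0.05: 1.275 − 0.425 = +0.85. With the fractions swapped: −1.275 − 1.70 = −2.98.

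**Simulation of the SAP 5.3.1 model.** SD 15, 20,000 runs, no true effect, direction of imbalance chosen to favour CPAP:

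| Common change | Missing, lower/higher arm | Bias towards CPAP | False positives for CPAP (nominal 2.5%) | Total type I error |
|---|---|---|---|---|
| 4 | 5%/10% | 0.2 | 2.9–3.0% | 4.8–4.9% |
| 8.5 | 5%/10% | 0.4 | 3.7–3.8% | 5.3% |
| 4 | 5%/20% | 0.6 | 4.3% | 5.7% |
| 8.5 | 5%/20% | 1.3 | 7.4–7.5% | 8.0–8.1% |

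Reversing the imbalance gives 0.2 to 1.3 points against CPAP. Observed-case regression held 4.7–5.3% total error in every null scenario.

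**Missing CPAP patients worsen.** Take 20% missing per arm, controls unchanged, observed CPAP patients falling 8.5 and missing ones rising 8.5. The truth is 0.8 × 8.5 − 0.2 × 8.5 = 5.1. The no-change rule gives 0.8 × 8.5 = 6.8. Own-arm mean and observed cases both give 8.5.

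**Missingness related to baseline.** Carrying a high baseline forward ignores regression to the mean. With no common change, 10% missing per arm and the odds of missing doubling per SD of baseline burden in controls only, the bias towards CPAP is 0.45 points under no-change (5.5% total error), 0.50 under own-arm mean (8.5%) and 0.01 for observed cases (5.0%). With the same relation but a common fall of 8.5, 10% missing in control and 20% in CPAP, no-change is 0.47 against CPAP and own-arm mean 0.44 towards it.

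**Own-arm mean check, missingness unrelated to baseline.** It removes the drift bias, but filled-in values are treated as observed. Type I error is 6.7–7.1% at 5%/10% missing, 8.4–9.0% at 5%/20%, 8.2% at 10% in each arm and 11.8% at 20% in each arm.

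**Median-regression fallback.** With a skewed burden (gamma, mean and SD 34, capped at 100; 1,000 runs), the bias towards CPAP is 1.2 points for a 25% common change at 5%/20% and 0.5 for a 25% fall at 5%/10%. False positives for CPAP are only 2.4–3.0%: the bias carries over, the error inflation does not.

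**The case against.** The rule is conservative in the scenario the SAP plans for, and with missingness unrelated to baseline, equal missingness and no effect it has no bias. Burden comes from an implanted recorder, so little should be missing, and stopping CPAP does not make it missing. The 8% figure needs a common change as large as the whole target effect plus a fourfold imbalance in missingness; no document supports either. All of this stands, and it limits the size of the problem rather than the error in the label.

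The own-arm mean check is also useful. A gap between it and the primary result would flag the drift problem. But it assumes that missing patients change like observed patients in their arm, so it never tests anything worse for CPAP. The Per Protocol analysis does not fill the gap: it removes patients with no device use from the CPAP arm only (SAP 3.3).

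A reader might infer that the check always errs in the same direction as the primary rule and slightly more. That holds with no common change and equal missingness; with a common change and unequal missingness the two can differ in size or sign. Nor is the check biased whenever missingness depends on baseline: the same relation in both arms at equal rates gave essentially no bias.

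**Conclusion.** The label is wrong as written: the no-change rule can favour CPAP and is not a worst case for it. The direction follows from the algebra. The sizes rest on the assumed drift, missingness and correlation, and run from about 0.2 points with total error near 5% to about 1.3 points with about 8% in the extreme case.

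A reader might infer that the rule generally favours CPAP, or that a positive primary result would be untrustworthy. The documents do not support that: they give no drift or missingness rates, the opposite imbalances work against CPAP, and recorder data should rarely be missing.

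The questionnaires may be more exposed, because the protocol flow chart has one post-randomisation questionnaire visit in Phase 1, so one missed visit is a missing outcome. That was not simulated, and SAP 2.4.1 treats those outcomes as supportive or exploratory.

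What remains is a gap in the plan: no analysis lets missing CPAP patients do worse than missing controls, and the one alternative imputation gives intervals that are too narrow.

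**What to change.** 1. In SAP 5.3.5, delete the worst-case sentence or qualify it with the conditions under which the rule is conservative.
2. In SAP 5.3.6, replace own-arm mean single imputation with an arm-specific delta or tipping-point analysis in which missing CPAP patients do progressively worse than missing controls, using a method that carries imputation uncertainty.
3. Beside the no-change result, report the same regression on patients with observed outcomes, or multiple imputation within arm.

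Making item 3 the primary analysis is optional. Observed-case analysis assumes missingness is unrelated to outcome given arm, site and baseline, and it overstates CPAP more than the no-change rule does if missing CPAP patients worsen (8.5 against 6.8, truth 5.1, in the example above). It would not cost power under the assumed inputs: at 20% missing per arm, 81% against 78% with no common change, 82% against 72% with an 8.5-point fall, and 82% against 79% with an 8.5-point rise.

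The cost is SAP text and a little more analysis code, with intervals slightly wider than under single imputation. No new data are needed. The flow diagram in SAP 4.1 already has a line for patients "randomised and excluded from the primary analysis", with reasons.

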5.3.6 Sensitivity Analyses

1. The primary outcome will be analysed on the Per Protocol Set.
2. Missing data will be imputed with the mean change in the respective treatment group. I.e., a patient in the CPAP group with missing data will be given a change for

STATISTICAL ANALYSIS PLAN for Effect of treatment of sleep apnea in patients with paroxysmal atrial fibrillation.

the missing outcome equal to the mean change in the CPAP group, and vice versa for patients in the usual care group.

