2.3 Sample size

The primary endpoint is a reduction of AF burden (% of time in AF) in the intervention group compared to control. We have defined a 25 % reduction of AF burden (% of time in AF) as a clinically significant effect. The extent to which treatment of AF will improve SA is unclear, and there are few data on the effects of treating SA on arrhythmia burden in patients with AF. With a mean time of 34% in atrial fibrillation and a standard deviation (SD) of 12%,¹ a power of 80% and a two-sided significance level of 5 % we will need at least 33 patients in each group. To allow for an increase in the standard deviation to 15%, we will include a total of 100 patients. No interim analysis will be performed.

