2.4 Statistical Framework

2.4.1 Hypothesis Test

This trial is designed to establish the superiority of treatment of CPAP over usual care for the total burden of atrial fibrillation in patients with paroxysmal atrial fibrillation and concomitant moderate-severe sleep apnea.

- The primary null hypothesis is that the change in the total burden of atrial fibrillation from baseline (one month prior to randomization) to the last three months of the intervention period is equal with CPAP treatment and usual care.
- The primary alternative hypothesis is that there is a difference in change in the total burden of atrial fibrillation from baseline (one month prior to randomization) to the last three months of the intervention period between CPAP treatment and usual care.

There is only one identified primary analysis in this trial. All other efficacy analyses will be regarded as supportive or exploratory.

STATISTICAL ANALYSIS PLAN for Effect of treatment of sleep apnea in patients with paroxysmal atrial fibrillation.

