5.3.7 Subgroup Analyses

The primary outcome and the secondary outcomes AFSS AF burden (#8 in Section 5.1.4), AFSS symptom score (#9), SF-36 physical (#11), SF-36 mental (#12), ESS sum score (#13), and FOSQ sum score (#14) will be analysed in the following subgroups:

- Male vs females
- Age below median vs. age above median
- Duration of AF below median vs. duration of AF above median
- Left atrium size below median vs. left atrium size above median
- BMI below median vs. BMI above median
- Patients that use the CPAP mask for more than 4 hours a night vs. patients that use the CPAP mask for less than 4 hours a night (no change in the usual care group)
- Patients who either have a DC cardioversion or start treatment of Flecainide, Dronedaron, or Amiodarone after inclusion vs. patients who do not have a DC cardioversion or start treatment of either Flecainide, Dronedaron, or Amiodarone after inclusion.

A comparison of the effect of CPAP between the subgroups will be analysed by adding a subgroup indicator variable and an interaction term between the subgroup and treatment to the linear regression model. A significant subgroup effect will be declared if the interaction term is statistically significant at the 5% level. Within- and between subgroup effects will then be reported with mean differences and 95% confidence intervals.

6 Safety Analyses and Adverse Events

At each follow up visit all serious adverse events will be recorded in the Viedoc database with description of adverse event, with start and end date of the event. Information will be provided on the severity, causality and expectedness of the adverse event

Investigator records the maximum intensity of each AE using the levels mild, moderate, severe or life-threatening. Applicable treatment given and outcome of event will also be recorded

The summary of events will be exported from the Viedoc database. The summary of number of events will be used, rather than number of patients. Safety variables will be tabulated and presented for all patients in the safety set.

STATISTICAL ANALYSIS PLAN for Effect of treatment of sleep apnea in patients with paroxysmal atrial fibrillation.

7 Statistical Software

Stata/SE 16.0 (StataCorp LLC, College Station, TX) will be used to perform the statistical analyses, except for the analyses of the dichotomous outcome, which will be done with Matlab R2014a (The MathWorks, Inc.).

8 References

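### The mean-change imputation in SAP 5.3.6 treats filled-in values as observed, so its confidence interval is too narrow and its P-value too small

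*SAP*

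**What the plan says.** The primary analysis (SAP 5.3.1) regresses AF burden in the last three months on treatment, site and baseline burden in the Full Analysis Set. For the output the SAP says: "The mean difference between the two treatment groups with a 95% confidence interval will be reported", with a P-value. SAP 5.3.2 applies the same model to the continuous secondary outcomes.

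The main missing-data rule, SAP 5.3.5, is: "Missing data will be imputed such that the patient with missing data will have no change from baseline on the missing outcome". The SAP describes this as a worst case for CPAP.

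SAP 5.3.6 lists two sensitivity analyses. Item 1 repeats the primary outcome in the Per Protocol Set. Item 2 reads: "Missing data will be imputed with the mean change in the respective treatment group". It adds that a CPAP patient receives a change for "the missing outcome equal to the mean change in the CPAP group, and vice versa for patients in the usual care group". Sections 5.3.1 to 5.3.6 mention no multiple imputation, random residual, bootstrap or other variance adjustment. Item 2 is also not restricted to the primary outcome, so on its wording it reaches the 14 continuous secondary outcomes in SAP 5.1.4, of which 12 are questionnaire scores.

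**The concern.** Item 2 is deterministic single imputation followed by a model that cannot tell imputed from observed values. Each imputed change equals its arm mean, so it contributes almost nothing to the residual sum of squares but is counted as a full patient. The residual variance is too small and the sample size too large. Both errors shrink the standard error.

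The stake is false reassurance. Zero-change imputation pulls the estimate towards no effect, and item 2 is its natural counterweight. Readers will set the two results side by side, and the P-value and interval of the second lean towards significance. The total of 100 is also tight: SAP 2.3 justifies it by a possible SD of 15% and states no allowance for missing outcomes, so borderline P-values are plausible.

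**Working it through.** **Inputs from the SAP.** 50 patients per arm (2.1); mean burden 34%, SD 12%, allowance to SD 15%, two-sided 5%, 80% power (2.3); relevant effect 25% of 34% = 8.5 points (2.3); regression on treatment, site and baseline (5.3.1).

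**Assumptions.** The missing fraction m, varied because neither document gives one; normally distributed burden; baseline to follow-up correlation 0.5 unless stated; outcomes missing at random, equally in both arms unless stated.

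**The plan's own figure.** The t-test sample size for 8.5 points gives 32.3 per arm at SD 12, rounded up to 33, and 49.9 per arm at SD 15, rounded up to 50. The stated 33 per group and total of 100 both reproduce.

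**Closed form.** Take n per arm and change-score SD s.

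- Reported SE after mean-change imputation: the variance shrinks to about s²(1 − m) while n is unchanged, so SE ≈ s√(2(1 − m)/n).
- Correct SE from the n(1 − m) observed patients: s√(2/(n(1 − m))).
- Ratio: 1 − m.
- Actual type I error: 2(1 − Φ(1.96(1 − m))). This is 6.0% at m = 4%, 7.8% at 10%, 11.7% at 20% and 17.0% at 30%.

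**Simulation of the SAP's regression under no effect** (50 per arm, 20,000 runs, both arms missing equally):

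| Missing per arm | Type I error | Reported SE / true SD of estimate |
|---|---|---|
| 2% | 5.5% | 0.98 |
| 4% | 6.3% | 0.95 |
| 6% | 6.7% | 0.93 |
| 10% | 7.8% | 0.90 |
| 16% | 9.8% | 0.84 |
| 20% | 11.9% | 0.79 |

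Correlations of 0.3 and 0.7 gave 7.6% at 10% missing and 11.1–12.1% at 20%. Complete-case regression and the zero-change rule both stayed at 4.6–5.2% throughout. Separate simulations, including one at SD 15, agreed within simulation error.

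**Loss in the CPAP arm only.** Type I error was 5.6%, 6.2% and 8.0% when 4%, 10% and 20% of that arm were missing. The overall fraction is then half as large, and the SE ratio follows the overall fraction: 0.89 when 20% of the CPAP arm is missing, against 1 − 0.10 = 0.90.

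**Interval width at SD 12.** The residual SD is 12 × √(1 − 0.5²) = 10.39.

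- 10% missing: correct half-width 1.988 × 10.39 × √(2/45) = 4.4 points; reported 4.0.
- 20% missing: correct half-width 1.992 × 10.39 × √(2/40) = 4.6 points (simulated 4.6–4.7); reported 3.8.

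**P-values.** A reported P of 0.05 on 96 degrees of freedom means t = 1.985. Multiply by (1 − m) and use the complete-case degrees of freedom:

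- 4%: 1.985 × 0.96 = 1.906 on 92, P ≈ 0.06.
- 10%: 1.985 × 0.90 = 1.786 on 86, P ≈ 0.08.
- 20%: 1.985 × 0.80 = 1.588 on 76, P ≈ 0.12.

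**Point estimate.** With a true reduction of 8.5 points, mean-change imputation and complete cases both return 8.5. Zero-change returns about 8.5 × (1 − m), that is about 7.7 at 10% and 6.8 at 20%.

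**The case against.** The strongest reply is that nothing in the trial is decided by item 2. The SAP says "There is only one identified primary analysis in this trial" and treats all other efficacy analyses as supportive or exploratory. Comparing the two point estimates, which is arguably the purpose of the exercise, remains informative. Section 5.3.6 does not itself say that an interval and P-value will be reported for item 2; that is inferred from 5.3.1 and 5.3.2. Missing AF burden may also be rare, given an implanted continuous recorder, a tolerability week before randomisation and five months of follow-up. At 2–4% missing the distortion is small.

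This limits the consequence but does not remove the error. Questionnaire outcomes do not share the recorder's protection, and no other output is specified for item 2.

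A second reply is that the Per Protocol analysis also drops some patients with missing data. It may, but it changes the population as well, and its requirement of at least one burden assessment does not make it a complete-case analysis.

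Third, the point estimate is only sound under random missingness. That is correct. Suppose 10% of the CPAP arm is missing, all from the upper half of baseline, with no true effect. Those patients average 12 × 0.80 = 9.6 points above the baseline mean, and the observed CPAP patients average (0.4 − 0.5) × 9.6/0.9 = −1.07. The imputed change is then 0.5 × 1.07 = +0.53, so each imputed outcome exceeds its expectation by 0.5 × 9.6 + 0.53 = 5.3 points. The arm mean moves by 0.10 × 5.3 ≈ 0.5 points. A simulation showed a shift of that size, with complete cases near zero. This further favours replacing item 2.

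Finally, the protocol calls AF burden highly variable, and SAP 5.3.4 allows for non-normal residuals: "a median regression (i.e. a quantile regression) will be performed instead of the linear regression". The figures here do not cover that fallback or the dichotomous outcomes.

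**Conclusion.** The concern holds. As written, item 2 attaches an interval that is too narrow and a P-value that is too small to an otherwise useful estimate, by a factor of about one minus the overall missing fraction. The mechanism and direction are certain. The size depends on a missing rate that the documents do not give: slight at 4% or less, material from about 10%, and more than double the nominal error rate at 20% in both arms. Loss confined to one arm roughly halves the inflation. The figures rest on normal data, linear regression and random missingness. The primary test is unaffected, so this is a correction that should be made, not one on which the trial's main conclusion depends.

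**What to change.** Replace item 2 of SAP 5.3.6 with the same regression (treatment, site, baseline) fitted to patients with an observed outcome. This keeps the contrast with the zero-change estimate and gives a valid standard error. State which outcomes it applies to; if the dichotomous ones are included, use the SAP 5.3.3 methods on patients with observed outcomes.

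An alternative is multiple imputation within arm from baseline value and site, pooled by Rubin's rules. SAP section 7 already provides the software: "Stata/SE 16.0 (StataCorp LLC, College Station, TX) will be used to perform the statistical analyses". In a check with 20 imputations and 2,500 runs, type I error was 5.1% at 10% missing and 4.0% at 20%, so it is slightly conservative at the higher rate. A delta shift could be added but is optional.

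The cost is one sentence, with no new data or software. The downside is wider intervals: at SD 12, about 0.4 points more in half-width at 10% missing and 0.8–1.0 at 20%. That is the precision the data support.
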